**Research Site:**  
University of Florida/Shands Emergency Department  
College of Medicine  
Department of Emergency Medicine  
[name]  
[name]  
[name]  
[contact]

- **Purpose of the Study and Background:**

**Study Purpose:** The purpose of this study is to *determine the effect of wound irrigation with IrriSept™ delivery system on abscess healing in healthy patients presenting to the Emergency Department (ED).*

The Specific Aims of the Study are:

- 1: To determine if use of pressurized irrigation with IrriSept delivery system in uncomplicated abscesses improves wound healing when compared to pressurized irrigation with normal saline.
- 2: To determine if use of IrriSept delivery system reduces (or eliminates) the need for oral antibiotics in patients with uncomplicated abscesses presenting to the ED.
- 3: To determine if use of pressurized irrigation with IrriSept delivery system in uncomplicated abscesses improves wound healing in patients that have MRSA-positive wounds compared to pressurized irrigation with normal saline.

**Background:** The current standard of care for the ED management of uncomplicated abscesses is to incise and drain (I&D), irrigate, and pack the wound. Oral antibiotics are commonly prescribed despite little evidence to support this practice. Based on published literature on this subject, a 6% to 16% re-infection rate occurs with this standard of care.

Since 2004, Irrimax Corporation has marketed a saline-based product (Max-101) which includes a novel compressible bottle design and splashguard. The product is used in EDs and other acute wound care sites to irrigate wounds with a pressurized dispersed stream of saline. In February 2009, Irrimax Corporation received notice that IrriSept, a new delivery system containing Chlorhexidine Gluconate (CHG), was cleared by the FDA for wound cleansing and debridement.

In early anecdotal studies conducted by Irrimax Corporation, an improvement in healing

rates and signs of infection were observed with use of these products. Most notably, a reduction in exudate from infected abscesses was observed within 24-48 hours of using IrriSept delivery system on wounds.

- **Criteria for Subject Selection:**

**Number of subjects:** The total number of consented ED subjects will be 628, 314 per arm. With an expected attrition rate of 66% for the return appointments, the total final number, who return for a 48-hour follow-up appointment and complete the entire study, will be 214 (n=214). The current attrition rate of subjects returning to the ED for recheck of uncomplicated abscesses at Shands/University of Florida ED is 66%.

A sample size of approximately 107 subjects in each arm will provide a power of 80% to detect a 20% improvement in subjects treated with IrriSept with an alpha of 0.05.

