**Primary Outcome Measures:**

Oral Antibiotics:

Oral antibiotics required at 48 hours?

Yes

No

Wound Improvement:

Wound improvement will be assessed on a 5-point Likert scale using the clinical scale outlined below.

- 1: Clinically resolved, no signs of active infection.
- 2: Markedly improved, resolving infection and healing.
- 3: Improved with some remaining signs of active infection.
- 4: Unchanged, stable without signs of worsening clinical infection.
- 5: Worsening conditions.

Exudate:

Exudate will be assessed using a 5-point Likert scale as outlined.

1 = none

2 = scant

3 = minimal

4 = moderate

5 = copious.

Patient Comfort:

Pain Scale – A subjective patient-assessed measure using a 10 cm Visual Analog Scale.

NO PAIN

MOST SEVERE PAIN

Secondary Outcome Measures:

Erythema – Circle the area of redness surrounding the abscess with a marker at treatment and at follow-up. Measure the longest and shortest axes of the most lateral edges.

Abscess Size:

Initial Measurement: [                    cm] x [                    cm]

1st Follow Up Measurement: [                    cm] x [                    cm]

2nd Follow Up Measurement: [                    cm] x [                    cm]

Warmth –

Yes

No

Fluctuance –

Yes

No

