**Data Analysis and Data Monitoring:**

The Statistical package for the Social Sciences (SPSS, v 17.0) will be used for data analysis. Descriptive statistics will be recorded as means  $\pm$  standard deviation or proportions as appropriate. Categorical variables will be compared using Chi-square and continuous variables will be compared with two-sided Student's t tests or analysis of variance as appropriate. For all analyses, a  $p$  value  $< 0.05$  will be considered significant.

**Data Monitoring:** The PI will be notified of all adverse events. There is no data monitoring committee for this study because the risk is low and no adverse events have emerged in previous cases and studies (in vivo and in vitro).

The sponsor employs a doctorally prepared registered nurse, with clinical trial/research experience, who holds an active Florida risk management license. She will provide desk top reviews for adverse events, if any.

**Data Storage and Confidentiality:** Information obtained in this research contains identifying patient information. Data collection forms will be secured in the ED in a locked file cabinet and removed when the patient has completed treatment (abscess in clinical stage 1 or 2) and stored in the PI's office in a locked file cabinet. The PI's office is locked at night assuring a double locked situation. Each unique patient ED visit will be assigned a code. Patient identifiers and key-codes will be kept exclusively within a password and encrypted protected spreadsheet that will be stored on the University of Florida Emergency Department server. Only those directly involved in this research will have access to the study data. Papers stemming from this work will not include identifying patient information. The key code will be destroyed at the end of the study.

**Patient Data Reporting:** The information from the patients will be "de-identified for research purposes" following HIPAA guidelines for the patient's privacy protection (in accordance with 45 CFR 164.502(d) and 164.514(a)-(c) of the Rule). The data will be collected on a paper copy as described above and assigned a unique identifier. De-identified forms will then be scanned and sent digitally to the sponsor.

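### Aim 3 retests the healing question in MRSA-positive wounds at the full 0.05 level, with no condition on Aim 1 and no exploratory label

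*Protocol*

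**What the plan says.** The protocol's Purpose of the Study and Background section introduces a numbered list with "The Specific Aims of the Study are". Aim 1 is to find out whether pressurized irrigation with IrriSept "in uncomplicated abscesses improves wound healing when compared to pressurized irrigation with normal saline". Aim 3 is to find out whether it "improves wound healing in patients that have MRSA-positive wounds compared to pressurized irrigation with normal saline". The intervention, comparator and outcome concept are the same. Only the population differs, and the Aim 3 population lies inside the Aim 1 population.

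The Data Analysis and Data Monitoring section gives the tests: "Categorical variables will be compared using Chi-square" and "continuous variables will be compared with two-sided Student's t tests or analysis of variance as appropriate". It then sets one threshold: "For all analyses, a $p$ value $< 0.05$ will be considered significant".

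The Number of subjects section plans one comparison: about 107 per arm, 80% power, a 20% improvement and an alpha of 0.05. It gives no separate size for MRSA-positive wounds and no expected MRSA share. The Wound Swab and Culture paragraph describes only the culture that defines the subset. Nowhere does the protocol order the aims, divide alpha between them or call the MRSA analysis exploratory.

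**The concern.** A subset analysis that stands as a formal aim, judged at the same level as the whole-population analysis, gives the healing question a second chance to succeed. Each test holds 5% separately, but the pair does not.

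The awkward outcome is a null result in all patients with p below 0.05 in the MRSA-positive patients. Under the stated rule, Aim 3 would then be answered yes although the comparison the trial was sized for had failed. No benefit overall but benefit in MRSA is an attractive finding, and it would rest on fewer patients than the planned 107 per arm.

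The problem does not depend on how many primary outcomes there are. If the trial settled on one healing outcome, that outcome would still be tested in two nested populations at full alpha.

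**Working it through.** **Inputs from the protocol.** Each test is at p < 0.05 (Data Analysis). The t tests are stated as two-sided and chi-square is non-directional. Allocation is 314 consented per arm, with about 107 per arm evaluable (Number of subjects).

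**Input not in the protocol.** The MRSA-positive share *f* is assumed to be 30–70%, with 10–90% as the outer range.

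**Step 1: the plan's own figure.** The protocol does not give the rates behind its 20% improvement. Taking 40% against 60%, the least favourable pair for a 20-point difference:

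- n = [1.96·√(2·0.5·0.5) + 0.842·√(0.4·0.6 + 0.6·0.4)]² / 0.20² = (1.386 + 0.583)² / 0.04 ≈ 97 per arm.
- With continuity correction: (96.9/4)·[1 + √(1 + 4/(96.9·0.20))]² ≈ 107 per arm.
- Attrition: 628 × 0.34 = 213.5, about 214.

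The stated size is therefore reproduced as a single two-sided test at 0.05. It makes no allowance for a second test of healing.

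**Step 2: joint behaviour of the two tests.** Write z₁ for the all-patient statistic and z₃ for the MRSA-positive statistic. With information proportional to patient numbers, z₁ = √f·z₃ + √(1−f)·z₋, where z₋ is the independent statistic in the remaining patients. The correlation of z₁ and z₃ is therefore √f. With no true effect the pair is standard bivariate normal, and three quantities follow:

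- A, either test significant in either direction: 1 − P(|z₁| ≤ 1.96 and |z₃| ≤ 1.96)
- B, either test significant in favour of IrriSept: 1 − P(z₁ ≤ 1.96 and z₃ ≤ 1.96)
- C, favourable in MRSA-positive wounds but not overall: B − 0.025

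| f | √f | A | B | C |
|---|---|---|---|---|
| 10% | 0.316 | 0.0949 | 0.0475 | 0.0225 |
| 30% | 0.548 | 0.0893 | 0.0447 | 0.0197 |
| 50% | 0.707 | 0.0831 | 0.0416 | 0.0166 |
| 70% | 0.837 | 0.0756 | 0.0378 | 0.0128 |
| 90% | 0.949 | 0.0648 | 0.0324 | 0.0074 |

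A single test at two-sided 0.05 gives A = 0.05 and B = 0.025. At shares of 30–70% both are inflated by the same factor: 0.0756/0.05 ≈ 1.5 to 0.0893/0.05 ≈ 1.8. Two independent tests would give an upper bound for A of 1 − 0.95² = 0.0975.

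**Step 3: check with binary data.** Simulated trials (400,000 per setting) with 107 per arm and a 50% rate in both arms gave A = 9.6%, 7.6% and 7.7%, and B = 4.7%, 3.8% and 3.8%, at f = 30%, 50% and 70%. The departures from the table reflect discreteness: the subset test alone rejected in 6.0%, 4.4% and 5.5% of trials.

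**Step 4: strength of the subset test.** With 107·f per arm and the assumed 40% against 60%, power in MRSA-positive wounds is about 36%, 54% and 69% at f = 30%, 50% and 70%.

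**Step 5: after a gate.** If Aim 3 is tested only when Aim 1 is significant, any false rejection requires one for Aim 1 first. A is then at most 0.05 for that outcome. Splitting alpha at 0.025 each would also control it (4.7% to 3.6% at shares of 20% to 80%), but would lower Aim 1's own level.

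**The case against.** The strongest objection is that test order and subgroup status are usually left to a statistical analysis plan, which is not shown here. The aims are also not plainly of equal weight: the trial is sized once, for all subjects, and no MRSA-specific outcome or subgroup test is described. Aim 3 is a claim about a narrower population, and whether separately stated aims need joint error control is partly a design judgement. These points limit the seriousness of the finding, but they do not remove it. The protocol is not silent: it sets a threshold and applies it to all analyses, so a later plan that gated Aim 3 would have to depart from that rule.

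A reader might infer that the chance of falsely claiming improved healing exceeds 5%. The calculation does not support that. The 7.5–9% includes false results against IrriSept, while both aims ask about improvement. In that direction the pair stays below 5%, and the proper benchmark is 2.5%.

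A reader might also infer that erythema, abscess size, warmth and fluctuance open further routes to a healing claim under the same threshold. The protocol does not support that either. It lists them as secondary outcome measures (for example "Erythema – Circle the area of redness surrounding the abscess with a marker at treatment and at follow-up"), and no text lets any of them establish an aim.

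One practical objection stands in full. A gate cannot work until Aim 1 has a single named healing outcome, and the protocol lists several primary measures.

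**Conclusion.** The point holds as a matter of structure: a formal aim repeats Aim 1 in a subset, under a blanket 0.05 rule, with no gate and no exploratory label. Its size is moderate. At shares of 30–70% the inflation is 1.5- to 1.8-fold, whether counted in both directions or only in favour of IrriSept. The exact figures depend on the assumed MRSA share, but the direction does not, since the two-sided rate exceeds 5% at every share from 10% to 90%. The figures cover this pair of tests on one healing outcome, with no true effect and information proportional to patient numbers. They leave out any further multiplicity from the several primary measures. The protocol should be changed here, but the Aim 1 comparison itself is unaffected.

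**What to change.** In the Data Analysis and Data Monitoring section, replace the blanket rule for these two aims with a fixed order:

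1. Name the one healing outcome and visit that answers Aim 1, for example the five-point wound improvement scale at 48 hours.
2. Test Aim 1 on that outcome at two-sided 0.05.
3. Test Aim 3 on the same outcome and visit, in MRSA-positive wounds, at two-sided 0.05 only if Aim 1 is significant.
4. If Aim 1 is not significant, report the MRSA-positive estimate with its 95% CI as exploratory, with no claim of significance.

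This takes a few sentences and no extra patients, visits or data. Aim 1 keeps its full alpha and power. There are two costs. The sponsor must commit to a single healing outcome for Aim 1, which the protocol has not yet done. And a real benefit confined to MRSA-positive wounds could be reported only as exploratory if Aim 1 fails.

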**Gender of Subjects:**

Male and female subjects will be included. Pregnant women or women who think they may be pregnant will be excluded.

**Age of Subjects:**

Immunocompetent patients aged 12 and older with uncomplicated abscesses will be eligible for study inclusion.

[figure not shown]
**Racial and Ethnic origin:**

There are no exclusions based on racial or ethnic origin.

**Inclusion Criteria:**

Immunocompetent individuals, 12 years of age or older, with an uncomplicated abscess are eligible for study inclusion. An uncomplicated abscess is defined as  $\leq 8$  cm of induration (defined as firmness to touch) at the greatest diameter with  $\leq 4$  cm of surrounding erythema (redness). A defined area of central fluctuance may or may not be present. Please see diagram below. The patient must be able to answer questions, be

medically stable as defined by the ED physician, and participate voluntarily in the study.

#### **Exclusion Criteria:**

Patients with any of the following are excluded:

- Currently receiving antibiotics or received antibiotics within the last 72 hours.
- Evidence of systemic infection (fever, aches, chills, nausea)
- Requires admission to the hospital for infection or for any other reason(s).
- Abscess caused by a human or animal bite.
- Prior history of hypersensitivity or allergy to Chlorhexidine Gluconate (CHG).
- Immunodeficiency (Examples: HIV Positive, Crohns Disease, Systemic Lupus Erythematosus, Addison's disease, psoriasis, splenectomy, leukemia, cancer on chemotherapy)
- Currently on any immune-modifying medication. (Examples – prednisone, antivirals)
- History of chronic skin infection ( 3 or more in the past year).
- Chronic medical problem, for example end-stage heart, liver, kidney or lung disease, diabetes mellitus, peripheral vascular disease, history of organ transplant
- Mental illness including but not limited to substance abuse, dementia, schizophrenia or mentally handicapped or challenged.

- Incarcerated.
- Patient is pregnant or thinks she may be pregnant.

**Vulnerable Subjects:**

Children older than 12 years of age, students, and employees may be included in the study, not because they are targeted, but because they may need care for abscesses.

**• Methods and Procedures:**

The study will be a prospective, randomized, controlled, double-blind, 2-arm study.

**General Study Design:** The two arms of the study will include an IrriSept arm and a normal saline arm. *Irrisep will be used to irrigate the abscess wound of patients in one arm of the study. In the second or normal saline arm, patients will have the abscess irrigated with normal saline using the same proprietary abscess irrigator cap in both arms.* The population will be randomly divided between the two arms. IrriMax will use a table of random numbers to randomize the study devices. Each device will be coded prior to being sent to the study site. IrriMax and the PI will have access to the code in case of an adverse event. Both IrriSept and the proprietary abscess irrigator cap are FDA cleared (Appendix A- include 510K)

Example: The randomizer indicates that bottles 3, 4, 5 contain treatment and 1,2,6 contain control or saline. The study site will use devices in order, but are blinded to treatment or control device. The informed consent forms will be numbered and the device number and informed consent number will match.

Bottle	Code	Randomizer
1	120120	control
2	120121	control
3	120121	Treatment
4	120121	Treatment
5	120122	Treatment

6	120123	control

This study will target healthy, immune-competent patients over 12 years of age with moderate abscesses that are treated on an outpatient basis. The patient who presents with an uncomplicated abscess and meets inclusion criteria will be approached for informed consent. Following consent to participate in the study, the patient will undergo abscess I &D using standard techniques and standard of care. A culture of the wound will be obtained and sent for microbiology analysis as defined by standard of care. The patient will be randomly assigned to group 1 or group 2. For the study to be double-blinded, both arms will use the same FDA-cleared device – a proprietary abscess irrigator cap for abscess irrigation. Group 1 will be irrigated with the *IriSept* delivery system and group 2 will be irrigated with normal saline. Both study arms will undergo a saline rinse step since according to the FDA clearance, *IriSept* requires the saline rinse step. Patients will have their abscesses photographed before, after initial treatment, and at each follow-up. Patients in this study will not receive antibiotics as part of their initial wound management. Those requiring antibiotics on the initial visit will be excluded from the study.

**Technique:** To achieve the double blind objective, the solution in both arms of the study will be applied under pressure using a proprietary abscess irrigator cap that delivers irrigant at a pressure of 7-8 psi as currently recommended. Bottles will be labeled with numbers only and codes for these numbers will be kept in the sponsor's corporate office. Study staff and patients will not be able to distinguish the control from the treatment because the solutions will look the same.

The prescribed treatment technique for both arms of the study is the following:

- 1: Employ universal precautions when cleansing open wounds, to include but not limited to gloves and eye protection.
2. Thoroughly cleanse the skin overlying the abscess with chlorhexidine swabs.

- 3: Anesthetize the skin overlying the abscess with 1% lidocaine.
- 4: Make a linear incision into the abscess cavity at a point of maximal fluctuance or in the center of induration if no fluctuance.
- 5: Insert forceps or other blunt instrument into abscess cavity and break up loculations. (if required)
- 6: Insert the tip of the irrigator cap into the abscess at the incision site.
- 7: Thoroughly cleanse entire abscess ensuring that exudate is clear and the solution contacts all inner surfaces of the abscess cavity.
- 8: Repeat until 450 cc of irrigant is used and the abscess is clear of exudate.
- 9: Wait at least one minute.
- 10: Rinse the abscess using the same technique as above with an equal volume of normal saline.
- 11: Loosely pack the abscess cavity with plain packing strip.
- 12: Apply a non-occlusive dressing to the wound.

After initial treatment, the physician will complete the patient data collection form through the "treatment" section and ensure that the patient understands the requirements for follow-up return and immediate return for worsening. The patient will follow-up every 48 hours for repeat examination until clinical resolution. This practice of frequent follow-up is consistent with the current standard of care. At each visit, the physician will complete the patient data collection form examining for fever, wound exudate, erythema, induration, warmth, fluctuance, pain, and abscess reformation. If at the first 48-hour evaluation, the patient's abscess is in category 1 or 2 (see Wound Resolution scale below), then the clinical data collection is complete. If the patient is in category 3, 4, or 5, there will be additional data collection every 48 hours until the patient's abscess is in category 1 or 2.

If signs of worsening or systemic infection are present, appropriate antibiotic treatment will be given. If necessary, a surgical consultation will be obtained or the patient will be admitted to the hospital for further treatment. This is at the discretion of the treating physicians.

**Wound Swab and Culture:** The abscess cavity will be cultured at presentation to assess the types of bacteria present with specific testing for MRSA. Wound culture is consistent with the current standard of care. MRSA positive isolates will be sent to the Emerging Pathogens Institute at the University of Florida for DNA fingerprinting and identification of specific MRSA isotypes.

**Data Collection:** Patients will be evaluated at 48 hours and at 48-hour intervals until abscess healing. The wound will be compared to previous data collected for wound exudate, erythema, induration, warmth, fluctuance, and pain. If the patient requires antibiotics, this will be recorded. Results from the wound culture and MRSA culture will also be recorded.

**Primary Outcome Measures:**

Oral Antibiotics:

Oral antibiotics required at 48 hours?

Yes

No

Wound Improvement:

Wound improvement will be assessed on a 5-point Likert scale using the clinical scale outlined below.

- 1: Clinically resolved, no signs of active infection.
- 2: Markedly improved, resolving infection and healing.
- 3: Improved with some remaining signs of active infection.
- 4: Unchanged, stable without signs of worsening clinical infection.
- 5: Worsening conditions.

Exudate:

Exudate will be assessed using a 5-point Likert scale as outlined.

1 = none

2 = scant

3 = minimal

4 = moderate

5 = copious.

Patient Comfort:

Pain Scale – A subjective patient-assessed measure using a 10 cm Visual Analog Scale.

NO PAIN

MOST SEVERE PAIN

Secondary Outcome Measures:

Erythema – Circle the area of redness surrounding the abscess with a marker at treatment and at follow-up. Measure the longest and shortest axes of the most lateral edges.

Abscess Size:

Initial Measurement: [                    cm] x [                    cm]

1st Follow Up Measurement: [                    cm] x [                    cm]

2nd Follow Up Measurement: [                    cm] x [                    cm]

Warmth –

Yes

No

Fluctuance –

Yes

No

